## RESEARCH STRATEGY

---

### A. BACKGROUND

**Asthma is a major cause of preventable disease burden (PCORI Methodology Standard RQ-3).** More than 25 million people in the U.S. have asthma, including 8% of adults and 9% of children, with significant racial and income disparities in prevalence. Morbidity from asthma is substantial, causing 10.5 million healthcare visits, 479,000 hospitalizations, and 3,100 deaths in 2009. Low income and racial/ethnic minority patients are more likely to experience adverse outcomes, leading to four times as many hospitalizations and five times as many deaths in blacks than whites, and this gap has been increasing. Guidelines recommend controller medications such as inhaled corticosteroids (ICS), leukotriene antagonists (LTA), or combination ICS and long-acting  $\beta_2$ -agonists (LABA) that are proven to improve asthma control and quality of life, prevent exacerbations, and reduce need for oral corticosteroids, emergency department (ED) visits, hospitalizations, and deaths due to asthma. However, many patients do not use daily controller medications, with 14-20% of individuals not filling prescribed controller medications once. Poor adherence to asthma controller medications increases the risk for adverse clinical outcomes. Increased levels of cost-sharing for asthma medications that lead to reduced adherence have also been associated with adverse downstream outcomes such as increased rates of asthma exacerbations, oral steroid bursts, and asthma-related ED visits and hospitalizations.

**Patients are increasingly faced with high levels of cost-sharing through high-deductible health plans (HDHPs).**

Compared with traditional plans, HDHPs have lower premiums but subject most services to annual deductibles of at least \$1000. HDHP membership more than quadrupled from 2006 to 2015 and 46% of workers now have HDHPs. HDHPs with associated Health Savings Accounts (HSAs) enable enrollees to use pre-tax dollars to pay for medical care. To qualify to include an HSA, HDHPs must have federally-regulated minimum annual deductibles (individual/family: \$1300/\$2600), and must include all care under the deductible except for select preventive services. As of early 2013, over 15 million people had HSA-HDHPs, with rates of uptake increasing rapidly, especially among large employers. HDHPs are also increasingly prevalent among enrollees in the ACA's health insurance exchanges.

**Patients experience substantial barriers to accessing needed medications for chronic conditions such as asthma due to cost-sharing.** Numerous studies suggest that high cost-sharing is associated with lower use of both non-essential and essential health care, including medications for chronic diseases. Among adults reporting difficulty paying medical bills, more than half said they had difficulty paying for prescription drugs. Studies in adults have shown that increased cost-sharing is associated with decreased use of important asthma medications. The few studies in pediatric populations have also shown reduction in use of asthma medications with increased cost-sharing. Evidence is limited on the impact of cost-sharing on rescue medications for asthma. Two studies have found that higher out-of-pocket (OOP) costs for bronchodilators were associated with decreased use for adults and children; our recent work found that higher copayments did not lead to decreased albuterol use for children relative to those without a copayment change, but did result in higher OOP costs (Figure 1).

**Families are increasingly concerned about OOP costs that can strain family budgets and lead to intra-familial trade-offs.** OOP costs from one family member can lead to delayed/forgone care for other family members, and high family OOP expenditures have been associated with lower rates of initiation of expensive medications. Some data suggest that parents prioritize their children's health care over their own when faced with financial pressures. Our research found that both adults and children are at increased risk for delayed/forgone care due to cost when faced with high deductibles, and that the risk is greater for healthy adults in families with chronically ill children, and for healthy children in families with chronically ill adults. In another study, we found that having a greater number of children in the family increased risk of financial burden among health insurance exchange plan enrollees, the majority of whom had HDHPs.

[figure not shown]
**HDHP enrollees are at risk for cost-related underuse of medications, especially in HSA-HDHPs.** Our research team was among the first to conduct studies of modern HDHPs, including more recent studies using the large, national dataset that we propose to use for the current project. We found that a switch to a HDHP was associated with fewer ED visits and hospitalizations, especially for low socioeconomic status (SES) enrollees; no change in rates of well-child visits and screenings for breast, cervical, and colorectal cancer, all of which were exempt from the deductible; and pronounced reductions in colonoscopy among low SES members. Other early studies of HDHPs without HSAs

demonstrated decreased utilization of both appropriate and inappropriate services, including prescription drugs. HDHP plans are also associated with greater patient out-of-pocket spending for care for families with chronic conditions. Patients with asthma are at particular risk from deductible costs, as controller and rescue medications are expensive branded drugs, costing \$140-\$307 a month for some inhaled steroids and \$30-60 for CFC-free albuterol inhalers without available lower-cost generic substitutes. HSA-HDHPs have been associated with decreased adherence for medications for asthma and other chronic conditions. In survey studies, we found that families in HDHPs were more likely than those in traditional plans to report health care-related financial burden and delayed/forgone care due to cost for both adults and children. In our qualitative studies, families reported challenges understanding and using HDHPs.

**Cost-sharing required by HSA-HDHPs has the potential to exacerbate disparities in access to medications for patients with asthma.** Some studies suggest that the impact of increased cost-sharing is greater for low-income populations, who are more likely to experience delayed/forgone care due to cost in HDHPs. Low-income, Hispanic, and African-American populations are more likely to report cost-related underuse of medications and other health care, and increases in copayments for chronic medications have a greater negative impact on adherence for low-income patients. However, one of our studies found that both lower and higher-income populations experience reductions in utilization in HDHPs.

**Increasing adoption of Preventive Drug Lists (PDLs) has the potential to preserve use of important asthma medications by patients in HSA-HDHPs.** Insurance plans increasingly seek to develop value-based health insurance designs (VBID) that include low or no cost-sharing for high-value services. In 2008, 19% of large employers used VBID strategies for medications in their health insurance offerings. The strategy of exempting medications from the deductible as part of a PDL is becoming increasingly popular among employers and health plans. PDLs are lists of medications for primary and secondary prevention (including asthma controllers and rescue medications) that are exempt from the deductible and available at reduced or no cost. Evidence is mixed about the impact of reducing or eliminating copayments for medications. Some studies of diabetes and cardiovascular medications demonstrated modest improvements in adherence and reductions in OOP costs, no change in adverse outcomes, and attenuation of racial/ethnic disparities. In HDHPs without HSAs, when medications have been excluded from the deductible and copayments applied instead, we found that prescription drug use for patients with asthma was preserved. We have also found this pattern in our ongoing national study of diabetes and HDHPs (1U58DP02719). However, in other studies, exempting medications from the deductible or eliminating copayments did not improve or

**Figure 1. Impact on OOP costs from a co-pay increase for albuterol inhalers**

**Exposed group had increased co-pays after a policy change mandating branded CFC-free albuterol inhalers. Control group maintained prior generic co-pay levels.**

preserve utilization of medications, including asthma medications. PDLs are a unique, readily adoptable VBID feature available with HSA-HDHPs with the potential to be substantially more powerful than previously studied VBID programs in traditional plans or HDHPs without HSAs because of the greater potential OOP cost differential for enrollees in HSA-HDHPs plans. However, we lack evidence about the impact of PDLs in HSA-HDHPs.

**Addressing gaps in evidence (RQ-1) on strategies to support patients in HDHPs is a priority area for PCORI.** Most studies of HSA-HDHPs or VBID have looked at medications globally or for conditions that are largely asymptomatic, such as hypertension. Only a few such studies focus on medications for symptomatic conditions like asthma; of these, none assess downstream effects on asthma-related clinical outcomes or disparities. Many studies of cost-sharing effects on asthma medications, especially those focusing on pediatric populations, have relied on weaker observational designs. Use of populations with a choice of health plan types and a lack of matched comparison groups create limitations due to selection bias in some of these studies. For some HSA-HDHP or VBID studies that include asthma medications, generalizability has been limited by inclusion of populations that come from a single employer or only include adults. The few studies on HSA-HDHPs or VBID that include dependents have not explicitly evaluated the impact on children or considered intra-familial effects. Findings of no or only modest changes in asthma medication use in some studies of cost-sharing, HDHPs without HSAs, or VBID may reflect relatively small copayment changes, and may underestimate experiences with HSA-HDHPs and PDLs in which cost differentials are much greater.

## **B. SIGNIFICANCE**

**The proposed project will improve the quality of evidence about HDHPs by being one of the first studies to examine the effect of free preventive drugs in HSA-HDHPs on asthma medication use and adverse asthma outcomes.** PDLs are especially relevant to asthma patients, given their frequent need for medications that can have short and long-term impact on symptoms and morbidity. Our focus on asthma is unique among studies of chronic conditions in HSA-HDHPs and PDLs because asthma affects both adults and children, requires both preventive and symptomatic medications, and does not have available generic lower-cost alternatives in key medication classes.

**As one of the first studies to explore adult-child differences and intra-familial tradeoffs that occur with increased financial pressures in HSA-HDHPs, this project will provide data on outcomes that affect parents and caregivers in families with one or more members with asthma.** Most HDHP and VBID research has focused on individual adults. However, many people obtain insurance as a family, and over 60% of HDHP enrollees are in family plans. Health care decisions involve trade-offs to balance family health care needs and costs against a family budget. Some studies of HDHPs have included data on dependents, but these have not addressed child-specific adherence or outcomes. We lack data to know if worrisome findings from adult-focused studies apply to the same extent in children.

**Findings from the proposed research will have immediate practical uses for patients, families, clinicians, employers, health insurers, and policy makers who are keen to find strategies to obtain insurance coverage with lower premiums while avoiding cost barriers to needed asthma care (RQ-3).** This project will provide crucial, patient- and family-centered evidence about health insurance strategies that are already being delivered in real-life settings. Opportunities are readily available to implement policy changes stemming from our findings. Given that HSA-HDHPs are standardized to meet federal policies for HSAs, and that PDLs covering a set of common, important medications have been already implemented by some insurers nationally, our findings can easily be generalized and translated into practice in other settings. If HSA-HDHPs with PDLs promote asthma medication adherence and better health outcomes, employers and health insurers could quickly shift to such designs. Findings can inform the health insurance choices of families with asthma as they seek affordable coverage that does not create cost barriers to obtaining needed care.

**This research focuses on outcomes that are increasingly of concern to patients with asthma, their families, and other stakeholders, namely cost barriers to obtaining needed asthma care (RQ-6).** Patients with asthma desire relevant information about the potential health and financial consequences of the multiple, complex insurance benefits options before them. Forward-looking employers, health insurers, and policy makers who wish to minimize unintended consequences of HSA-HDHPs are considering nuanced VBID strategies like PDLs to improve outcomes among patients with chronic conditions. Our research will evaluate these two “natural experiments” – employer-mandated switches to HSA-HDHPs and addition of PDLs that exempt key asthma medications from cost sharing – which increasing numbers of patients are facing. Letters of support from the Asthma and Allergy Foundation of America (AAFA), the Northeast

Business Group on Health (NEBGH), and America's Health Insurance Plans (AHIP) demonstrate the relevance of our proposed research to patients and stakeholders.

## C. APPROACH

### Specific Aims

Asthma is one of the most common serious chronic diseases of adults and children in the United States, affecting 18.7 million adults and 6.8 million children. Despite guidelines and evidence of their effectiveness in preventing adverse outcomes such as sick days, ED visits, and hospitalizations, adherence to recommended asthma controller medications is low. Cost is an important barrier to non-adherence to asthma medications. Employers are increasingly adopting HDHPs particularly those that qualify for HSAs, which subject most medications to deductibles rather than copayments as in traditional coverage. HSA-HDHPs can thus lead to forgone care due to cost, including clinically appropriate services such as asthma medications. As a response, value-based insurance designs have been proposed to promote high-value care by reducing or eliminating cost-sharing for these services. One common example is a PDL that can accompany HSA-HDHPs, which exempts certain chronic medications from the deductible to promote adherence. PDL's have become increasingly prevalent in HSA-HDHPs offered by employers, and many PDLs include asthma controller and rescue medications. Evidence suggests only a small adherence benefit when VBID reduces out-of-pocket (OOP) costs for already low-cost preventive medications in traditional plans without high deductibles. However, under HSA-HDHPs, where OOP costs are higher and the potential reduction by a PDL much more meaningful, we lack evidence on the response to PDL cost-sharing reductions among asthma patients. With the increasing prevalence of HSA-HDHPs, PDLs have the potential to improve controller medication adherence for both adults and children, which could improve asthma outcomes and reduce downstream costs. Lower asthma cost burden could mitigate cost-related trade-offs for families in HSA-HDHPs who must balance health care and other costs within a family budget.

In this project, we intend to evaluate the impact of two important developments in the health insurance landscape, HSA-HDHPs and PDLs, on medication use, clinical outcomes, and patient experiences for adults and children with asthma. We will take advantage of a rolling cohort of over 621,000 adults and 310,000 children with asthma who receive employer-sponsored coverage from a large national insurer between 2004 and 2017. We will employ a rigorous quasi-experimental interrupted time-series (ITS) and difference-in-differences (DiD) designs to examine the effect of being switched by an employer from HSA-HDHPs without PDLs to HSA-HDHPs with PDLs compared to controls who remain in HDHPs without PDLs. We will compare changes in medication use and patient-centered clinical outcomes (asthma-related ED visits and hospitalizations) for adults and children and within families. Qualitative interviews with patients with asthma in HDHPs will provide more in-depth patient-reported data on health care decision making and experiences in these plans, which will inform quantitative analyses. The overarching goal of this research is to provide needed evidence – including data gathered directly from patients – on whether pairing PDLs with HSA-HDHPs can mitigate cost barriers and improve patient-centered outcomes for adults and children with asthma. Our Specific Aims are:

1. To understand health care decision making and experiences of families with asthma under HSA-HDHPs and PDLs
2. To examine the impact of HSA-HDHPs with and without PDLs on use of asthma controller and rescue medications, and on adverse clinical outcomes (asthma-related ED visits and hospitalizations), overall and for vulnerable subgroups (low-income and racial/ethnic minority patients)
3. To examine the extent to which the response to HSA-HDHPs and PDLs is affected by the presence of other family members with asthma or other chronic conditions
4. To examine the impact of HSA-HDHPs with and without PDLs on out-of-pocket (OOP) costs for patients and families with asthma

With input from patients with asthma and other stakeholder partners, the proposed project will focus on patient-centered outcomes related to asthma care in new insurance designs. This research will meet a pressing need to understand the impact of a readily adoptable health insurance innovation that has major potential to improve asthma medication adherence and outcomes. Findings will advance the goal of developing and implementing insurance designs to promote access to high-value health care services and improve clinical outcomes while avoiding burdensome costs for families.

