## **Predictors and Covariates**

Table 2 shows the main predictors and covariates we will use in the proposed study for propensity matching to create study cohorts (CI-1, 4-5), predicting or adjusting outcomes, or stratifying analyses. Our primary predictor variables include study period and insurance type. Study period indicates the one-year period before or up to three years after the index date. Insurance type includes: 1) HSA-HDHP without PDL; 2), HSA-HDHP with PDL; and 3) traditional plan.

Other co-variates include asthma severity in the baseline period using the HEDIS definition for persistent asthma (see above under Study Population), and using chronic oral corticosteroid therapy (180+ days in the prior year) or any use of omalizumab in the baseline year to define severe asthma. To estimate co-morbidity, we will use the well-established Johns Hopkins Adjusted Clinical Groups (ACG) scores which use ICD-10 codes in the baseline period to calculate a standardized morbidity score in a specified time period. We will measure the presence of other chronic conditions from claims data in the baseline year using the Johns Hopkins ACG system. We will also measure whether enrollees have COPD as a co-morbidity, as there can be overlap with COPD and asthma, and use of similar medications.

A unique innovation of our study is the availability of data linkages (IR-2) with consumer data from a

major credit reporting company linked to insurance claims from our data vendor, Optum. Consumer data elements include total household income, net

worth, and race/ethnicity. We will combine self-reported race/ethnicity data from credit card and loan applications with data from Optum on surname analysis for identifying Hispanic or Asian ethnic groups and geocoding to derive race/ethnicity from census data. We will also use census-based indicators for neighborhood education and poverty levels. Other variables used to propensity-match cohorts and adjust for confounding will include sex and age; state/region of residence; individual versus family plan; baseline number of outpatient visits, presence of an inpatient hospitalization, and total expenditures; employer size (number of employees); and average employer baseline expenditures per capita (CI-1, 4-5).

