### **Methods to monitor and address missing data (MD- 1-3, 5)**

We have identified the following 5 variables as exhibiting data missingness (MD-1) in our dataset for this study:

- Variable 1: Geocoded poverty level
- Variable 2: Geocoded education level
- Variable 3: Member-level income level
- Variable 4: Member-level net worth
- Variable 5: Member-level deductible Level

**Missing poverty, education, income, and net worth data:** We will use 3 methods to accommodate missingness (MD- 2-3): (a) multiple imputation, (b) modeling missingness as a member-level characteristic, and (c) excluding members with missing data. If findings differ, we will present results using all 3 methods in manuscripts or attached appendices. We will use SAS procedures PROC MI and PROC MIANALYZE to impute the missing individual level covariates and conduct the statistical analyses under the assumption of missing at random. The SAS procedure PROC MI will impute the missing variables (including individual net worth, income level, poverty level and education level) using other available variables such as age, gender, census block level income, poverty, education etc. Then we will use PROC MIANALYZE to analyze the imputed data. We will also explore certain Bayesian imputation techniques to handle missing data in case missing is not at random and compare the results. If the degree of missingness for member-level credit report data is found to be too great, we will still be able to use geocoded poverty and education census block-level data, for which missingness has been less than 1% in the study team's prior work using this data source.

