In all statistical models, we will include key individual-level predictors from Table 2 to adjust for potential confounding. To determine the impact of HSA-HDHP with and without PDLs on vulnerable populations (RQ-4) and test for heterogeneity of treatment effects among vulnerable populations (HT-1-4), we will first perform stratified analyses, comparing outcomes between intervention and control subgroups defined by the binary measures of the risk factors of interest (low income, minority race/ethnicity, moderate-severe asthma, presence of other chronic conditions (including co-morbid diagnosis of COPD; we will also conduct analyses limited to ages 4-50 to remove the effect of COPD co-morbid diagnoses), high ACG morbidity). We hypothesize that these vulnerable subgroups will have worse adherence, more frequent adverse clinical outcomes, and higher OOP costs. We will use three-way interaction terms (insurance type \* study period \* subgroup) to test for statistical differences between subgroups in the impact of the change to an HSA-HDHP with PDL vs. remaining in a traditional plan. Heterogeneity of treatment effect analyses for these key variables will be reported along with overall findings from the combined population. Given that we will be conducting sub-group analyses to test for heterogeneity of treatment effect based on race/ethnicity and income using three-way interaction terms, we elected to separate the analyses of heterogeneity of treatment effect by age group into Aim 3 (described below), rather than add a fourth interaction term to the analyses in Aim 2. In Aim 2 analyses, we will include

both adults and children together, with age included as a co-variate. Given that health plan cost-sharing policies in HSA-HDHPs and PDLs usually apply across enrollees regardless of age, and given that health plans, employers, policy makers, and families must make decisions about HSA-HDHPs and PDLs for both adults and children together, we felt it was important to evaluate the impact at the overall population level.

**Aim 3:** to examine the extent to which the response to HSA-HDHPs and PDLs is affected by the presence of other family members with asthma or other chronic conditions.

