There are multiple factors that affect adherence to asthma medications and asthma outcomes in addition to insurance type and cost barriers. We are able to measure many of these factors using claims (e.g. baseline disease severity, age, gender, income, race/ethnicity) but not others (e.g. attitudes, provider factors, competing demands). Claims data also do not allow measurement of important asthma outcomes such as symptom days, missed school/work days, or lung function. The Aim 1 qualitative study will be able to contribute these additional dimensions of non-financial barriers to adherence and asthma outcomes, however. Despite its limitations, claims data permit population-level measurement of important and commonly used downstream indicators of asthma complications such as asthma-related ED visits and hospitalizations which we have experience measuring in our prior asthma studies. The use of geocoding and surname analysis limits our ability to determine member race/ethnicity at the individual level, but provide excellent population-level estimates when used together. We will assess the degree of missingness for these fields in our study, but do not anticipate that it will be problematic given that annual missingness of geocoded SES variables in the study team's prior work using this data source has been less than 1% (MD-1).

Sharing of asthma medications within a family may affect the accuracy of measurement of an individual's medication use based on claims data. However, only 16% of children share or borrow asthma medications, usually bronchodilators. Unlike other studies of cost-sharing and medication use in the literature, our study can capture this effect by measuring family-level medication use and OOP costs. Utilization of medications and other health services in HSA-HDHPs may be affected by the amount of funds in a member's HSA, which can be used to pay deductible costs. Data on HSA balances is not available for all members, however.

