The patient population for **Aims 2-4** will consist of patients with asthma enrolled in a large U.S. commercial health plan from 2004-2017. We will capitalize on one of the largest and most geographically diverse observational datasets of commercially-insured asthma patients, including adults and children from all 50 states over 14 years. The size and geographic reach of this health plan will allow our study to be representative of a wide range of sociodemographic groups, geographic locations, and delivery systems. Our study will analyze retrospective de-identified data routinely collected by the health plan, and the study team will not contact or recruit patients for these Aims. We will systematically identify eligible patients using claims-based algorithms that have been used in multiple studies to identify patients with asthma. The characteristics and numbers of patients whose claims data will be analyzed are described above in Tables 2 and 3.

Our study will specifically examine potential disparities for low-income and racial/ethnic minority populations in response to high levels of cost sharing in high deductible plans, based on prior evidence that these groups may be adversely affected (RQ-3). We will identify patient subgroups based on income and race/ethnicity using our dataset's credit report information and imputed information on ethnicity based on member surname and neighborhood SES data. We will use claims-based measures employed in other studies to identify patient subgroups based on asthma severity, other chronic conditions, and morbidity who may be likely to be adversely affected by high cost-sharing(RQ-3).

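### The Aim 2 racial/ethnic tests treat a partly inferred race/ethnicity class as known, with no step for misclassification, so the racial difference in plan effect may be biased in either direction

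*Combined protocol and SAP*

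**What the plan says.** The Specific Aims make plan effects "overall and for vulnerable subgroups (low-income and racial/ethnic minority patients" part of Aim 2. The Aim 2 hypothesis is that racial/ethnic disparities widen in an HSA-HDHP without a PDL and lessen when a PDL is added.

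Predictors and Covariates gives the sources of the variable. "We will combine self-reported race/ethnicity data from credit card and loan applications", it says, with "surname analysis for identifying Hispanic or Asian ethnic groups and geocoding to derive race/ethnicity from census data". Section D (Patient Population) describes the same variable as credit report information plus "imputed information on ethnicity based on member surname and neighborhood SES data".

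Table 2 codes race/ethnicity as five fixed categories (Hispanic, Asian, Black, White, Other) and uses it as predictor, matching variable and stratifier. The Aim 2 analysis plan begins with stratified analyses, "comparing outcomes between intervention and control subgroups defined by the binary measures of the risk factors of interest (low income, minority race/ethnicity" and further factors), then tests a three-way interaction of insurance type, study period and subgroup.

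Generalizability and Limitations states that "The use of geocoding and surname analysis limits our ability to determine member race/ethnicity at the individual level". The same sentence goes on to defend the two methods, which in its view fall short for single members "but provide excellent population-level estimates when used together". It adds that missingness of these fields will be assessed. The missing-data section opens with "We have identified the following 5 variables as exhibiting data missingness (MD-1) in our dataset for this study"; race/ethnicity is not one of the five.

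**The concern.** The caveat in the limitations section concerns individual-level assignment, and the Aim 2 strata and interaction are an individual-level use. A good population-level estimate of how many members are Black or Hispanic does not ensure that the right members are in each stratum.

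As described, surname analysis serves to identify Hispanic and Asian members. Without self-report, a Black member's class would therefore rest mainly on the neighbourhood. The plan states no accuracy figure for the assignment, no self-reported share, no analysis confined to self-reported members and no bias analysis. By contrast, it reports 97.0% sensitivity and 96.2% specificity for imputed deductible levels and plans a split-sample test of that algorithm.

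Two errors are possible. A null interaction could be reported as no racial disparity when misclassification has diluted one. Or a difference that belongs to poorer neighbourhoods could be reported as racial. The results are meant for employers, insurers and policy makers, so either error matters.

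**Working it through.** The plan gives no figure for the racial/ethnic test, so there is none to reproduce. The steps below show the direction of the bias and its possible range.

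**1. Inputs from the documents (Table 4).** The race total is 3,420 + 12,059 + 90,170 + 5,515 = 111,164. This equals the Table 3 group sizes plus the Table 1 interviews: 4,222 + 16,888 + 18,000 + 72,000 + 54 = 111,164. The Black share is 12,059/111,164 = 10.8%. The non-White share is (111,164 − 90,170)/111,164 = 20,994/111,164 = 18.9%.

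**2. Inputs that are assumed.** Sensitivity 0.5 to 0.9 and specificity 0.90 to 0.99 for the assigned class. The documents give neither.

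**3. Errors unrelated to the plan effect.** The observed difference in effect between strata is the true difference times PPV + NPV − 1. With true share q:

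- share classed as the subgroup: c = q × sens + (1 − q)(1 − spec)
- PPV = q × sens / c; NPV = (1 − q) × spec / (1 − c)

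Worked case, Black versus the rest, sensitivity 0.7, specificity 0.95, using the unrounded share 0.1085: c = 0.0759 + 0.0446 = 0.1205; PPV = 0.0759/0.1205 = 0.630; NPV = 0.847/0.8795 = 0.963; factor = 0.593.

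| Contrast | Factor at 0.7 / 0.95 | Range over the assumed inputs |
|---|---|---|
| Black vs rest (10.8%) | 0.59 | 0.32 to 0.90 |
| Non-White vs White (18.9%) | 0.70 | 0.42 to 0.93 |

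The second row is nearer to the planned binary minority test. It is still only a proxy, because Table 4 counts Hispanic ethnicity separately.

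**4. Errors that follow neighbourhood.** Let A be the part of the plan-effect difference due to race and B the part due to living in a given type of neighbourhood. Then true difference = A + B × d and observed difference = A × r + B × n. Here d is the excess of that neighbourhood type among true minority members, and r and n are the excesses of true minority members and of that neighbourhood type among those classed as minority. An exact expected-value calculation at 18.9% non-White, with overall sensitivity 0.65 and specificity 0.95, has d = 0.35, r = 0.69 and n = 0.60 (all assumed):

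| A | B | True | Observed | Observed/true |
|---|---|---|---|---|
| −3 | 0 | −3.00 | −2.06 | 0.69 |
| −3 | −3 | −4.05 | −3.87 | 0.96 |
| −1 | −3 | −2.05 | −2.49 | 1.22 |
| 0 | −3 | −1.05 | −1.80 | 1.72 |

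In a variant of the last row with weaker segregation the ratio was 2.99. The bias can therefore go away from zero. Table 2 lists neighbourhood education, poverty and SES as predictors, but the race model has no term letting them modify the plan effect.

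**5. Would membership probabilities cure it?** This was simulated for Black versus the rest: neighbourhood Black share beta-distributed with mean 10.8% and intraclass correlation 0.20, 0.35 or 0.50; classed Black if the share is at least 50%; self-report 0%, 30% or 60% (all but the mean assumed). Entries are the estimated share of the true gap:

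| Neighbourhood modifier | Fixed class | Probability |
|---|---|---|
| None | 0.51 to 0.91 | 1.00 |
| Equal to the race effect | 0.84 to 0.97 | 1.08 to 1.67 |

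The probabilities here were perfectly calibrated, so calibration alone does not protect them. Repeating the comparison in self-reported members returned the true gap in every scenario that had self-report, given that self-report is accurate and unselected.

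**6. What a null could hide.** Take Table 3's 2.0-point detectable PDC difference for the PDL contrast as given, and assume the same variance and subgroup split in both groups. The detectable interaction is then about 2.0/√(q(1 − q)): 6.4 points for Black versus the rest and 5.1 for non-White versus White. If only 0.7 of the difference is seen, the true one must be about 6.4/0.7 = 9.2 or 5.1/0.7 = 7.3 points. The plan's hypothesised overall changes are 5-9% (PDC, switch to an HSA-HDHP without a PDL) and 1-4% (fills, switch to a PDL).

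**The case against.** The plan is open about the limitation, uses some self-report, and plans to assess missingness of these fields. All of that stands, but missingness and misclassification are different problems, and disclosing a limitation does not tell the analyst how to read the interaction.

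Four stronger readings are tempting and are not supported:

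- *The plan admits that it cannot determine individual race.* It says that its ability is limited, and part of the data is self-reported.
- *The bias is toward zero.* That needs errors unrelated to the plan effect, which geocoding does not guarantee (step 4).
- *The missing-data list contradicts the rest of the plan by omitting race/ethnicity.* That list covers variables with missing values. An assigned but wrong class is measurement error, so the omission shows only that no remedy is placed there.
- *Entering probabilities removes the bias.* It does so only if neighbourhood has no effect of its own (step 5).

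It is also fair to object that Black versus the rest is not the planned contrast. The planned test pools minority groups, confusing one minority group with another does no harm to it, and Hispanic and Asian members found by surname may be classed better. The Black-versus-rest figures are therefore illustrations and not estimates for that test.

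**Conclusion.** The point holds in a limited form. A partly inferred race/ethnicity class is used as a fixed individual attribute in the Aim 2 strata and interaction, and nothing in the plan handles misclassification. Attenuation is likely if assignment errors are unrelated to the plan effect. If neighbourhood itself modifies that effect, the racial difference may be overstated or may be a neighbourhood difference, so the direction is not guaranteed.

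The size cannot be fixed from the documents, because the accuracy and the self-reported share are not given. The illustrations span about 0.3 to 0.9 of the true Black-versus-rest difference with independent errors, and exceed 1 in some neighbourhood scenarios. The main Aim 2 results in the whole population do not depend on this point. It is a change that should be made, because it bears on a stated hypothesis and is cheap.

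**What to change.** In the Aim 2 analysis plan, with matching notes in Predictors and Covariates and in Generalizability and Limitations:

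1. Report the share of race/ethnicity values from each source, and the agreement of the inferred class with self-report where both exist.
2. Prespecify, as a sensitivity analysis, a repeat of the race/ethnicity strata and interaction tests in members with self-reported race/ethnicity.
3. Add a neighbourhood-SES by insurance type by period term to the race model.
4. State that a null interaction on the assigned class will not be read as no disparity, nor a positive one as purely racial, unless the self-report analysis agrees.
5. Optionally, add membership probabilities or multiple imputation of race/ethnicity as a further sensitivity analysis, with the neighbourhood term included. These should not replace the main analysis on the claim that they remove the bias.

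The cost is SAP wording and modest programming on data the plan expects to hold, provided the source of each value is flagged. The self-reported subset is smaller, so less precise, and may be selected because it comes from credit and loan applicants. Its result therefore needs its own caveat.
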